8 CONSENT OF ADULTS

Review the following definitions before answering the questions in this section.

CONSENT

is the process of informing potential subjects about the research and asking them whether they want to participate. It usually (but not always) includes an opportunity for subjects to ask questions. It does not necessarily include the signing of a consent form. This question is about the consent process.

CONSENT DOCUMENTATION

refers to how a subject's decision to participate in the research is documented. This is typically obtained by having the subject sign a consent form.

CONSENT FORM

is a document signed by subjects, by which they agree to participate in the research as described in the consent form and in the consent process.

ELEMENTS OF CONSENT

are specific information that is required to be provided to subjects.

PARENTAL PERMISSION

is the parent's active permission for the child to participate in the research.

Parental permission is subject to the same requirements as consent, including written documentation of permission and required elements.

SHORT FORM CONSENT

is an alternative way of obtaining written documentation of consent that is most commonly used with individuals who are illiterate or whose language is one for which translated consent forms are not available.

WAIVER OF CONSENT

means there is IRB approval for not obtaining consent or for not including some of the elements of consent in the consent process.

WAIVER OF DOCUMENTATION OF CONSENT

means that there is IRB approval for not obtaining written documentation of consent.

8.1 Groups Identify the groups to which your answers in this section apply.

Adult subjects

Parents who are providing permission for their children to participate in research

→ If you selected **PARENTS**, the word "consent" below should also be interpreted as applying to parental permission and "subjects" should also be interpreted as applying to the parents.

8.2 The consent process. This series of questions is about whether you will obtain consent for all procedures except recruiting and screening and, if yes, how.

The issue of consent for recruiting and screening activities is addressed in [question 4.6](#). You do not need to repeat your answer to question 4.6.

a. Are there any procedures for which you will not obtain consent?

No

Yes

→ If yes, use the table below to identify the procedures for which you will not obtain consent. "All" is an acceptable answer for some studies.

Be sure to consider all research procedures and plans, including future contact, and sharing/banking of data and specimens for future work.

Group ¹	Describe the procedures or data/specimen collection (if any) for which there will be NO consent process	Reason why you will not obtain consent	Will you provide subjects with info about the research after they finish?	
			YES	NO
FP clinic	Preliminary Clinic Review	Clinic manager assent		
FP clients	FP data register	We will not have direct access to the FP clients and will be obscuring names of clients in image capture.		
FP clinic	Randomized trial	Clinic manager assent for participation		
				
				

Table footnotes

1. If your answer is the same for all groups you can collapse your answer across the groups and/or procedures.

b. Describe the consent process, if you will obtain consent for any or all procedures, for any or all groups. Address groups and procedures separately if the consent processes are different.

Be sure to include:

- *The location/setting where consent will be obtained*
- *Who will obtain consent (refer to positions, roles, or titles, not names).*
- *Whether/how you will provide an opportunity for questions*
- *How you will provide an adequate opportunity for the subjects to consider all options*

Assent of participation of FP clinics: Letters of introduction from Mombasa County will be sent to individual clinics. Following this, clinic managers will be approached and asked for voluntary participation in the initial performance evaluation of the clinic. They will also be advised that they may be asked to continue to participate in the randomized controlled trial, and that trial participation could include assignment to either the intervention or control arm. The study will be explained in detail. After answering any questions, we will ask the manager to provide verbal assent for participation of the clinic and staff.

Individual FP clinic staff: Study staff will obtain informed consent for participation in in-depth interviews. They will be reassured that they are free to decline to participate without penalty. The consent process will follow the Standard Operating Procedure that is in place for all of our research activities in Mombasa (see Appendix). This consent process includes the following procedures:

- Ensure that the consent process is taking place in a private area.
- Use the informed consent checklist as a guide throughout the consent process and enter the time at the beginning of the sheet.
- Give the consent form for the client (FP clinic staff member) to read in their language of choice (English or Kiswahili) and allow enough time for the staff member to read the consent form.
- After the potential participant reads the consent/has it read to her, review the key points.
- Ask the potential participant if they have any questions and discuss any questions or concerns.
- Clarify any misunderstanding and determine eligibility.
- Once eligibility is determined the counselor can proceed with the consent process.
- Sign the informed consent checklist and retain if the staff member enrolls
 - The potential participant should sign and date first and must write her/his own name. The person obtaining consent signs last.

Potential participants must demonstrate their understanding of key concepts about the informed consent before signing. Specific questions used to assess understanding may include items such as:

1. Please describe what your role will be in this research study?
2. Is participation in these interviews voluntary?
3. If you do not participate, will this reflect negatively in your work evaluations or job status?

The consent form will include the possibility of negative consequences regarding employment if staff members are identified as providing negative information about the workplace. We will also explain how we plan to keep these data confidential.

FP clinic clients: We are requesting a waiver of consent for the FP clinic clients, as we will only be abstracting information that will be de-identified.

c. Comprehension. Describe how you will ensure or test the subjects' understanding of the information during the consent process.

Consents will be written in both English and Kiswahili with study staff performing the consent process being fluent in both English and Kiswahili. In order to assess comprehension of potential participants for the in-depth interview, we will ask similar questions as follows:

1. Please describe what your role will be in this research study?
2. Is participation in these interviews voluntary?
3. If you do or do not participate, will this reflect negatively in your work evaluations or job status?

d. Influence. Does your research involve any subject groups that might find it difficult to say "no" to your research because of the setting or their relationship with you, even if you don't pressure them to participate?

Examples: Student participants being recruited into their teacher's research; patients being recruited into their healthcare provider's research, study team members who are participants; outpatients recruited from an outpatient surgery waiting room just prior to their surgery.

	No
	Yes

→ If yes, describe what you will do, for each of these subject groups, to reduce any effect of the setting or relationship on their decision.

Examples: a study coordinator will obtain consent instead of the subjects' physician; the researcher will not know which subjects agreed to participate; subjects will have two days to decide after hearing about the study.

e. Ongoing process. For research that involves multiple or continued interaction with subjects over time, describe the opportunities (if any) you will give subjects to ask questions or to change their minds about participating.

FP clinics will have the opportunity to withdraw the study at any time.

8.3 Written documentation of consent. Which of the statements below describe whether you will obtain documentation of consent? NOTE: This question does not apply to screening and recruiting procedures which have already been addressed in [question 4.6](#).

Documentation of consent that is obtained electronically is not considered written consent unless it is obtained by a method that allows verification of the individual's signature. In other words, saying "yes" by email is rarely considered to be written documentation of consent

a. Are you obtaining written documentation of consent for:

None of your research procedures → Use the table below to provide your justification then go to [question 8.4](#).

All of your research procedures → Do not complete the table; go to [question 8.3.b](#).

Some of your research procedures → Use the table below to identify the procedures for which you will not obtain written documentation of consent from your adult subjects.

Adult subject group ¹	Describe the procedures or data/specimen collection (if any) for which there will be NO documentation of consent	Will you provide them with a written statement describing the research (optional)?	
		YES	NO
FP clinic	Preliminary clinic review assent by clinic manager		
FP clients	Data abstraction from FP register with client names removed		
FP clinic	Randomized trial with assent by clinic manager		
FP clinic staff	Exit in-depth interviews during COVID19 social distancing guidelines		

Table footnotes

1. If your answer is the same for all adult groups or all procedures, you can collapse your answer across the groups and/or procedures.

8.4 Non-English-speaking or -reading adult subjects. Will you enroll adult subjects who do not speak English or who lack fluency or literacy in English?

No

Yes → If yes, describe the process you will use to ensure that the oral and written information provided to them during the consent process and throughout the study will be in a language readily understandable to them and (for written materials such as consent forms or questionnaires) at an appropriate reading/comprehension level.

Consent documents will be translated from English into Kiswahili and then back-translated to English to confirm consistency in language and appropriate cultural context.

a. Interpretation. Describe how you will provide interpretation and when. Also, describe the qualifications of the interpreter(s) – for example, background, experience, language proficiency in English and in the other language, certification, other credentials, familiarity with the research-related vocabulary in English and the target language.

Study staff performing the semi-structured interviews and in-depth interviews will be fluent in both English and Kiswahili and consent documents will be in both languages.

All study staff are fluent in English and Kiswahili, so there is no interpretation required between staff and participants. In the course of a study that involves trained health professionals, we do not expect to identify individuals in coastal Kenya who do not speak one or both of these languages fluently.

b. Translations. Describe how you will obtain translations of all study materials (not just consent forms) and how you will ensure that the translations meet the UW IRB's requirement that translated documents will be linguistically accurate, at an appropriate reading level for the participant population, and culturally sensitive for the locale in which they will be used.

Consent documents will be translated from English into Kiswahili and then back-translated to English to confirm consistency in language and appropriate cultural context.

8.5 Barriers to written documentation of consent. There are many possible barriers to obtaining written documentation of consent. Consider, for example, individuals who are functionally illiterate; do not read English well; or have sensory or motor impairments that may impede the ability to read and sign a consent form.

a. Describe your plans (if any) for obtaining written documentation of consent from potential subjects who may have difficulty with the standard documentation process (that is, reading and signing a consent form). Skip this question if you are not obtaining written documentation of consent for any part of your research.

Examples of solutions: Translated consent forms; use of the Short Form consent process; reading the form to the person; excluding individuals who cannot read and understand the consent form.

Consent documents will be translated from English into Kiswahili and then back-translated to English to confirm consistency in language and appropriate cultural context.

8.6 Deception. Will you deliberately withhold information or provide false information to any of the subjects?

No
 Yes

→ If yes, describe what information and why.

Example: you may wish to deceive subjects about the purpose of the study.

a. Will you debrief the subjects later? (Note: this is not required.)

	No
	Yes

→ If yes, describe how you will debrief the subjects. Upload any debriefing materials, including talking points or a script, to the **Consent Form and Recruitment Materials** SmartForm of **Zipline**.

8.7 Cognitively impaired adults, and other adults unable to consent.

a. **Cognitively impaired adults and other adults unable to consent.** Do you plan to include such individuals in your research?

Examples: individuals with Traumatic Brain Injury (TBI) or dementia; individuals who are unconscious, or who are significantly intoxicated.

	No
	Yes

→ If no, go to [question 8.8](#).

→ If yes, answer the following questions.

a.1. Rationale. Provide your rationale for including this population in your research.

a.2. Capacity for consent / decision making capacity. Describe the process you will use to determine whether a cognitively impaired individual is capable of consent decision making with respect to your research protocol and setting. If you will have repeated interactions with the impaired subjects over a time period when cognitive capacity could increase or diminish, also describe how (if at all) you will re-assess decision-making capacity and consent during that time.

a.3. Permission (surrogate consent). If you will include adults who cannot consent for themselves, describe your process for obtaining permission (“surrogate consent”) from a legally authorized representative (LAR).

For research conducted in Washington State, see the [SOP: Legally Authorized Representative](#) to learn which individuals meet the state definition of “legally authorized representative”.

a.4. Affirm. Describe whether assent will be required of all, some, or none of the subjects. If some, indicate which subjects will be required to assent and which will not (and why not). Describe any process you will use to obtain and document assent from the subjects.

a.5. Dissent or resistance. Describe how you will identify the subject's objection or resistance to participation (including non-verbal) during the research, and what you will do in response.

8.8 Consent-related materials. Upload to the **Consent Forms and Recruitment Materials** SmartForm of **Zipline** all consent scripts/talking points, consent forms, debriefing statements, Information Statements, Short Form consent forms, parental permission forms, and any other consent-related materials you will use.

- Translations must be included. However, you are strongly encouraged to wait to provide them until you know that the IRB will approve the English versions.
- Combination forms: It may be appropriate to combine parental permission with consent, if parents are subjects as well as providing permission for the participation of their children. Similarly, a consent form may be appropriately considered an assent form for older children.
- For materials that cannot be uploaded: upload screenshots or written descriptions that are sufficient to enable the IRB to understand the types of data that will be collected and the nature of the experience for the participant. You may also provide URLs (website addresses) or written descriptions below. Examples of materials that usually cannot be uploaded: mobile apps; computer-administered test; licensed and restricted standardized tests.

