Qualitative data: We will carry out half-day direct continuous monitoring observations of FP service delivery at each intervention clinic to identify patient flow bottlenecks, assess wait times, and observe quality of staff interaction with patients. Research teams will conduct open-ended semi-structured individual in-depth interviews (IDIs) with clinic managers and staff from each clinic to identify key health system factors perceived by respondents to influence clinic performance. In-depth interviews will focus on organizational values and goals, senior management roles and engagement, staff presence and expertise, communication, coordination, problem solving, and training (58). Detailed observation and interview notes will be collected and compiled. We anticipate that we would notify staff of the observation. If a staff member did not want to be observed, we would allow them to opt out. This could mean either avoiding observation in their work area, or not observing within that clinic, depending on what was required to respect the staff member's request. Interviews will also be recorded to check accuracy, clarify, and refine the final interview notes. The IDI and observation notes will be analyzed using Atlas.ti software to identify key themes (59).

Sequential process flow mapping: Process mapping is an essential component of quality improvement in healthcare (51), allowing workers to identify key areas for intervention. To develop sequential process flow maps, trained research assistants will work with staff at each intervention clinic to generate an initial draft of the map on paper. The map will then be transferred to an electronic format using Microsoft Visio. The document produced in this process will be reviewed again with FP clinic staff to insure that it is an accurate representation of the processes and to fine tune the flow map as needed.

Analysis of Data from Detailed Performance Review of Intervention Clinics

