Time-and-motion studies will be conducted over a two-week period at each site while the intervention is running at full capacity. A mentee trained in this process will collect data on the time required to complete each step of the SAIA process. Observing multiple visits will allow estimation of the average time taken for each step, and any time taken for research purposes (e.g. consent or assent of clinic staff members) will be subtracted from the estimated time needed for the intervention. Multiple providers and clients will be observed to capture the range of time required for a successful SAIA intervention. We anticipate that we would notify staff of the observation. If a staff member did not want to be observed, we would allow them to opt out. This could mean either avoiding observation in their work area, or not observing within that clinic, depending on what was required to respect the staff member's request. Through staff interviews and accounting for time available for the SAIA intervention, the number of patients supported by a clinic will be estimated. Together, the micro-costing data and the time-and-motion studies will be used to estimate the average cost of new HIV-positive and HIV-negative diagnoses.

Budget Impact Analysis

For BIA, we will consider direct program costs. Direct medical costs will be measured using established micro-costing methods, described above, to ensure that measurements of DOH costs reflect the opportunity cost of the resources used in delivering services. Further, the “top-down” approach of expense report collection will be compared with the “bottom-up” micro-costing approach to triangulate

and refine our cost estimates.

Data Analysis for Costing and Budget Impact Analysis

To the extent possible, we will use guidelines to facilitate standardization of cost data collection and reporting and to increase the transparency and generalizability of our results. For all key inputs and outputs, we will follow standard practices (57), including the guidelines by the Panel of Cost-Effectiveness in Health and Medicine (58). We will report on all costs using a recommended discount rate of 3% per year, as well as an alternative 5% discount rate and undiscounted inputs. We will conduct sensitivity analyses around key cost inputs to account for the uncertainty in our results.

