disclosure if the content of their interviews identified them as being in a particular position. Several steps will be taken to mitigate this risk in response to question 2.

FP clinic clients: For patients accessing care through FP clinics, the risks associated with seeking family planning services will not be different from the risks associated with seeking these services in the absence of the research. However, there is the potential for a loss of privacy by data abstraction from health records/register. Steps to mitigate this risk are detailed in response to question 2.

10.2 Reproductive risks. Are there any risks of the study procedures to men and women (who are subjects, or partner of subjects) related to pregnancy, fertility, lactation or effects on a fetus or neonate?

Examples: direct teratogenic effects; possible germline effects; effects on fertility; effects on a woman's ability to continue a pregnancy; effects on future pregnancies.

No → If no go to [question 10.3](#)

Yes → If yes, answer the following questions:

a. **Risks.** Describe the magnitude, probability, duration and/or reversibility of the risks.

b. **Steps to minimize risk.** Describe the specific steps you will take to minimize the magnitude, probability, or duration of these risks.

Examples: inform the subjects about the risks and how to minimize them; require a pregnancy test before and during the study; require subjects to use contraception; advise subjects about banking of sperm and ova.

If you will require the use of contraception: describe the allowable methods and the time period when contraception must be used.

c. **Pregnancy.** Describe what you will do if a subject (or a subject's partner) becomes pregnant

For example; will you require the subject to immediately notify you, so that you can discontinue or modify the study procedures, discuss the risks, and/or provide referrals or counseling?

10.3 Unforeseeable risks. Are there any research procedures that may have risks that are currently unforeseeable?

No

Yes → If yes, identify the procedures.

10.4 Subjects who will be under regional or general anesthesiology. Will any research procedures occur while subjects-patients are under general or regional anesthesia, or during the 3 hours preceding general or regional anesthesia (supplied for non-research reasons)?

No

Yes → If yes, check all the boxes that apply.

- Administration of any drug for research purposes

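### The consent waiver for family planning (FP) clients and the client risk list cover register abstraction only, yet two planned procedures also observe clients, with notice and opt-out for staff alone

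*Combined protocol and SAP*

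**What the plan says.** All references are to the combined protocol and SAP.

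- **Waiver request, 8.2b:** "We are requesting a waiver of consent for the FP clinic clients, as we will only be abstracting information that will be de-identified".
- **Table of procedures without consent, 8.2a:** clients appear once, for the FP data register. The reason given is "We will not have direct access to the FP clients and will be obscuring names of clients in image capture". The table in 8.3 on undocumented consent also lists clients only for register abstraction.
- **Client risks, 10.1:** one privacy risk is named: "However, there is the potential for a loss of privacy by data abstraction from health records/register".
- **Clinic observation, 5.1, Aim 1, Qualitative data:** study staff carry out "half-day direct continuous monitoring observations of FP service delivery at each intervention clinic". Besides looking at bottlenecks and waiting times, they are to "observe quality of staff interaction with patients".
- **Time-and-Motion Studies, 5.1:** these run for two weeks at each site. "Multiple providers and clients will be observed to capture the range of time required for a successful SAIA intervention".
- **Choice about being observed:** both 5.1 texts say that staff would be notified, and both say "If a staff member did not want to be observed, we would allow them to opt out". Neither gives clients a corresponding provision.

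**The concern.** A waiver has to be judged on an accurate account of what it covers. Here the request for clients as a group rests on the team doing nothing but abstracting de-identified records. Watching an encounter between a provider and a client, or timing a client's visit, is not record abstraction, so the ground given does not reach either procedure.

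What is at stake is the privacy of women attending a contraceptive service in which HIV counselling and testing are also offered. The presence of an observer is the most direct contact that the described procedures have with clients, and it is missing from the consent table, the waiver request and the client risks. The authors recognised that being observed calls for a choice, since they gave staff one. The client in the same encounter has none on paper.

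**Working it through.** No arithmetic applies, and the plan gives no figure to reproduce on this point. The check sets the texts side by side.

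**Step 1. What the waiver and risk texts cover.** Sections 8.2a, 8.2b, 8.3 and 10.1 all describe one client activity: abstraction from the register with names covered. Section 5.3 lists the data sources as registers and interviews and leaves out observation.

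**Step 2. What 5.1 has the team do.**

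| Procedure in 5.1 | Clients observed? | Fits the 8.2b ground (abstraction only)? | Notice and opt-out for staff? | Notice, permission or opt-out for clients? |
|---|---|---|---|---|
| Half-day clinic observation | Yes, staff-patient interaction | No | Yes | None stated |
| Time-and-motion study | Yes, clients are named | No | Yes | None stated |

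The count is 2 procedures that observe clients, 0 that fit the ground for the waiver, 2 with a staff opt-out and 0 with any client-facing provision.

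**Step 3. Does another section fill the gap?**

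- *9.1 (privacy).* It promises that procedures are explained to subjects before enrolment. Clients are not enrolled and their consent is to be waived, so the promise does not reach them. The form's own text in 9.1 defines privacy as control over others' access to oneself.
- *9.6b (data security).* Observation notes are encrypted and record roles in place of staff names. Client names and contact details are dealt with only for register scans. Encryption protects the notes. It gives the client no say over who is present.
- *8.2b and 8.2e (clinic level).* The manager assents for the clinic and its staff, and a clinic may withdraw. Neither is a client's permission.
- *10.1 (mitigation).* For steps that reduce client risk it points to question 2. Section 2 (Participants) contains no privacy measures.

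**Step 4. Can the waiver be read more narrowly?** Suppose that it is meant for the register alone. Client observation then has neither a consent process nor a waiver. On the wider reading it has a waiver whose stated ground is not true of it. The gap remains on both readings.

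**The case against.** The strongest reply is that the 8.2a table is organised by procedure. The no-direct-access reason sits in the register row, and for scanned registers with names covered it is fair. This stands. A reader might infer that the row itself is a false statement about the whole study, and the row does not say that. The defect is the missing row for observation, together with the word *only* in 8.2b.

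Second, clients are not wholly unprotected. Notes are encrypted, clinics may withdraw, and a staff opt-out can mean that a work area or a whole clinic is not observed. This also stands, so a reader who concludes that there is no safeguard at all goes too far. These measures are data security or help clients only incidentally.

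Third, the depth of exposure is not stated. A reader might infer that an observer sits in on HIV counselling or testing. No text places one there. The time-and-motion study is aimed at the steps of the SAIA process, many of which are staff work, although the same paragraph speaks of observing visits and names clients. The documents are also silent on what clients are told in practice, and the consent SOP cited in 8.2b is not available here. The finding is that nothing is stated, not that clients are known to be left uninformed.

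Fourth, timing. The COVID-19 disclaimer in 5.1 shows that this text dates from after Aim 2 had begun. The half-day observations belong to the start of Aim 1 and have probably been done. This limits the remedy for that procedure but does not remove the need to describe it correctly.

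Fifth, the activity may be minimal risk. Even so, the IRB needs an accurate description in order to decide that.

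**Conclusion.** The point holds as an inconsistency between what is planned and what the waiver and risk sections describe, with a real consequence for clients. Two procedures observe clients, neither fits the ground given for the waiver, and neither has a stated client-facing notice, permission or opt-out. It should be corrected, but it touches no estimand, outcome, analysis or sample size.

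The conclusion rests on reading the 5.1 sentences at face value, and on no client provision existing in uploaded material that is not part of the documents.

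Two stronger readings are not supported:

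- **A count of clients observed.** A reader might derive one from the county client volumes in 2.1. The plan gives no number of visits to be timed, and nothing says that every client at a clinic would be in view. Extending such a count to control clinics would also sit badly with the Randomization text in 5.1, which limits study involvement there to outcome ascertainment.
- **An effect on testing.** A reader might infer that observation deters women from testing and so affects the primary outcome. No text supports this.

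**What to change.** 1. **8.2b:** limit the client waiver to abstraction from the register.
2. **8.2a table:** add a client row for direct observation and time-and-motion work.
3. **10.1:** add observation to the client risks and say how it is mitigated. Bring the data sources in 5.3 into line at the same time.
4. **5.1, Time-and-Motion Studies, and the Aim 1 observation text for any session still to be done:** state that each client is told who the observer is, is asked for verbal permission, and has the same opt-out as staff, with no change to the service she receives.

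The alternative is to state in 5.1 that clients will not be observed. The aims of looking at staff-patient interaction and of timing client visits would then have to be dropped or reworded.

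The cost is a short script, an IRB modification and a few declined observations. Outcome collection from the registers and the analysis are unchanged.
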